7.3. Exclusion Criteria

If any of the following exclusion criteria are applicable to the subject or either eye, the subject should not be enrolled in the study.

- Subjects with history of previous ocular surgery.
- Subjects with topographic evidence of keratoconus, or ectasia.
- Subjects with autoimmune diseases.
- Subjects who are pregnant or nursing.
- Systemic disease likely to affect wound healing, such as diabetes and severe atopy.
- Any ocular disease (including un-controlled dry eye) which in the investigator's opinion would affect the outcome of refractive surgery.

The principal investigator reserves the right to declare a patient ineligible or nonevaluable based on medical evidence that indicates they are unsuitable for the trial.

Pregnancy has a known effect on the stability of refractions and visual acuity. As such, subjects who become pregnant during the study will not be discontinued but their data may be excluded from analyses of effectiveness.

8. STUDY DESIGN

8.1. Study Design

This study is a single site, single-arm, prospective, observational study of subject satisfaction, after successful bilateral LASIK surgery. Subjects will be assessed pre-operatively, operatively and at 1 week, 1 month, and 3 months post-operatively. Clinical evaluations will include measurement of visual acuity, manifest refraction, and topography, aberrometry, and administration of the OSDI and PROWL questionnaires.

The primary outcome measure will be the percentage of subjects satisfied (Completely Satisfied or Very Satisfied) with vision after Phorcides Planned Contoura LASIK based on PROWL Questionnaire preoperative vs postoperative (question #1 only).

Secondary outcome measures are as follows:

• Percentage of eyes with post-op spherical equivalent within +/- 0.50 D.

Exploratory outcome measures are as follows:

- Preoperative and postoperative higher order aberrations (spherical aberration and coma).
- Preoperative and postoperative responses on the PROWL questionnaire (Q2-Q33).
- Preoperative and postoperative OSDI scores.
- Correlation of postoperative OSDI score and responses on the postoperative PROWL questionnaire (Q1).

8.2. Methods Used to Minimize Bias

As a single-arm study there is no expected bias. Patient selection will be based on the patient's interest and the surgeon's opinion as to whether they are a suitable candidate for LASIK.

The measurement of visual acuity will be conducted in a systematic fashion to minimize bias. Individuals conducting visual acuity measures will be instructed to perform the same testing in the same fashion for all subjects, with the same level of encouragement to subjects. Questionnaire instructions will be provided to all patients in a similar manner.

All data collection will be completed through provided Case Report Forms (CRFs) or computer files generated by automated test equipment. All site personnel involved in the study will be trained in regard to conducting study-specific procedures.

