3. GENERAL INFORMATION

Objective	To determine the percentage of subjects satisfied (Completely Satisfied or Very Satisfied) with vision after Phorcides Planned Contoura LASIK. The hypothesis is that a high percentage of subjects receiving the Phorcides Planned Contoura LASIK will be satisfied with their vision		
	Phorcides Planned Contoura LASIK will be satisfied with their vision.		
Test Article(s)	WaveLight® EX500 Contoura laser		
Control Article(s)	None.		
Sample size	104 eyes of 52 subjects		
Study Population	Subjects 21 to 39 years of who are appropriate candidates for laser refractive surgery.		
Number of sites	One		
Study Design	Single site, single-arm, prospective, observational study		
Masking	None		
Variables	Primary: Percentage of subjects satisfied (Completely Satisfied or Very Satisfied) with vision after Phorcides Planned Contoura LASIK based on PROWL Questionnaire preoperative vs postoperative (question #1 only).		
	Secondary:		
	• Percentage of eyes with post-op spherical equivalent within +/- 0.50 D.		
	 Exploratory: Preoperative and postoperative higher order aberrations (spherical aberration and coma). Preoperative and postoperative responses on the PROWL questionnaire (Q2-Q33). Preoperative and postoperative OSDI scores. Correlation of postoperative OSDI score and responses on the postoperative PROWL questionnaire (Q1). 		
Duration / Follow-up	Preoperative to 3 months postoperative		

The study will be registered with clinicaltrials.gov.

The study will be conducted in compliance with the protocol, GCP and applicable regulatory requirements

4	TARLE	OF	CONTENTS
H .	IADLL	UF	CONTENTS

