5. INTRODUCTION

Phoreides reproducibly and accurately applies geographic imaging software to topographic corneal measurements, utilizes optical physics of lens theory, and the refractive effect of treating corneal irregularities.^{1,2} It allows for a vector analysis that accounts for anterior corneal astigmatism, posterior corneal astigmatism, manifest refraction measured astigmatism, and internal astigmatism into a suggested topography-guided treatment. Combining all these vectors and compensating for the postoperative spherical effect that can be directly impacted by the ablation profile of the corneal higher order aberrations yields a mathematical based surgical plan for the suggested treatment of the patient's refractive spherical magnitude, the astigmatic magnitude, and the astigmatic axis. Consequently, it is anticipated that Phoreides will prove to be a powerful surgical planning tool directly resulting in improved postoperative patient satisfaction with visual acuity and visual symptoms.

The decision to choose between a Phorcides derived Contoura LASIK ablation versus other various refractive procedures often times can be a difficult decision because of a lack of previous research analyzing patient satisfaction with their postoperative uncorrected visual acuity and visual symptoms. The purpose of this study is to determine the percentage of subjects satisfied with vision after Phorcides Planned Contoura LASIK.

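### Having a single arm does not remove bias: the unmasked, self-reported satisfaction rate is open to selection and response bias that no measure in Section 8.2 addresses

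*Combined protocol and SAP*

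**What the plan says.** Section 3 describes a "Single site, single-arm, prospective, observational study" and gives both masking and control as none. Sections 3 and 8.1 define the primary outcome as the percentage of subjects in the top two satisfaction categories of PROWL question 1, preoperative against postoperative.

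Section 8.2, on minimising bias, opens with "As a single-arm study there is no expected bias". The next sentence describes entry to the study: "Patient selection will be based on the patient's interest and the surgeon's opinion as to whether they are a suitable candidate for LASIK". Three measures in that section bear on this point:

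- visual acuity: "The measurement of visual acuity will be conducted in a systematic fashion to minimize bias", followed by detail on uniform testing and encouragement;
- the questionnaires: "Questionnaire instructions will be provided to all patients in a similar manner";
- staff: "All site personnel involved in the study will be trained in regard to conducting study-specific procedures".

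Elsewhere, Section 9.2.1 and Table 15.1 place a PROWL at the preoperative visit. Table 9.2-1 sets the 3-month visit, where the only postoperative PROWL is given, at 90 ± 20 days. Section 5 anticipates that the software will prove a planning tool "directly resulting in improved postoperative patient satisfaction with visual acuity and visual symptoms".

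**The concern.** The number of arms settles one thing only: whether unequal allocation can distort a comparison between arms. It has no bearing on who enters the study, how they answer a satisfaction question, or what the result can be compared with. Here all three are open. Subjects know what surgery they had, they report their own satisfaction within the treating practice, and no control group shares the same influences.

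The study's headline result is one satisfaction percentage. If some suitable candidates are not invited, or some subjects answer to please the team or to match their expectations, the percentage moves and the reader has no means of seeing it. Neither problem can be repaired once enrolment and the 3-month visit are over.

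**Working it through.** **1. The plan's own figures.** The plan gives no expected satisfaction rate and no allowance for bias, so there is no such figure to reproduce. Section 11 asks for 46 pairs for 90% power at a 5% level, with mean difference 25 and SD 50. With a standardised difference of 25/50 = 0.5, a two-sided paired t-test (noncentral t) needs 44 pairs for 90% power and has 91.3% power at 46. The stated number is therefore adequate on its own terms, but it deals with random error only.

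**2. Each safeguard against each source of bias.**

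| Feature of the plan | What it controls | What it leaves open |
|---|---|---|
| One arm | Allocation between arms | Selection, response, lack of comparator |
| Preoperative PROWL (9.2.1, Table 15.1) | Gives a starting level | Courtesy and expectation about the surgery, which can affect the postoperative answer differently |
| Fixed window, 90 ± 20 days (Table 9.2-1) | Timing of the answer | How and before whom it is given |
| Similar instructions (8.2) | Differences between subjects in what they are told | An influence common to all subjects |
| Staff training, CRF capture (8.2) | Errors of procedure and recording | Selection and response |

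**3. Questionnaire administration.** The 3-month visit refers to Section 9.3 for its assessments, including the questionnaires. Section 9.3 describes manifest refraction and visual acuity only. The text reviewed does not say who hands out PROWL, whether it is completed in private, whether it comes before the examination, or whether the operating surgeon sees the answers.

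**4. Selection.** Sections 7.2 and 7.3 set the criteria, and Section 8.2 adds patient interest and surgeon's opinion. Section 9.2.1 assigns subject numbers after consent, in order of enrolment. A candidate who met the criteria but was not invited, or who declined, therefore leaves no trace. No consecutive invitation or screening log is described.

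**5. Scale.** One subject who moves into the top two categories changes the rate by 1/46 = 2.2 points, or 1/52 = 1.9 points if all 52 are analysed.

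**6. Would a confidence interval reveal it?** This is an illustration on assumed values, not an estimate. Let the true rate be p, let reporting add b, and take n = 46. Coverage of an exact 95% interval is the sum, over x = 0 to 46, of the Binomial(46, p + b) probability of x for those x whose interval contains p.

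| Assumed true rate | b = 3 points | b = 5 points | b = 10 points |
|---|---|---|---|
| 80% | 96.2% | 92.9% | 68.8% |
| 85% | 92.4% | 85.1% | 40.6% |
| 90% | 96.3% | 90.5% | not shown (reported rate would be 100%) |

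A small shift would hardly matter at this sample size. A large one would, and the interval would give no sign of it.

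**7. Attribution.** The objective in Section 6 is descriptive: a percentage after the procedure. Section 5 anticipates an improvement that results directly from the software. With no control, the first can be delivered and the second cannot be shown.

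**The case against.** The strongest reply is that the sentence is loose wording in a section that goes on to list measures against bias, so the authors did not behave as if there were none. That is fair. A reader might infer that the false premise is the reason the primary outcome lacks protection; the documents give no reason, and the point does not depend on one.

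Several other parts of the reply stand:

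- Suitability for LASIK partly defines the target population. Unsuitable patients lie outside the question, so their absence is not bias. Nothing shows that eligible candidates will be passed over; the plan simply has no way of showing whether they were.
- A reader might infer that the care given to visual acuity is misplaced because acuity is not a listed endpoint. It is an eligibility criterion (Section 7.2), and the same type of chart is used for the refraction (Section 9.3.1) from which the secondary endpoint is derived.
- Masking patients is not feasible with one arm, and the plan openly declares that there is none.
- Section 5 states an anticipation, not a finding.
- Sections 12, 14.1 and 16, which by their titles concern confidentiality and publication, were not in the text reviewed, nor were the questionnaire forms. They probably do not govern private completion, but this could not be checked.

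What the reply does not meet is that every listed measure either acts equally on all subjects or concerns something other than the satisfaction answer. None reduces or exposes a shift common to the whole sample.

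**Conclusion.** The statement in Section 8.2 is wrong and should be replaced, and two inexpensive changes to conduct should go with it. Selection, response and no-comparator bias are all to be expected in this design. The existing safeguards deserve credit but do not reach them.

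The likely direction is upward. That is a reasoned inference: it assumes that patients tend to answer favourably to the team that treated them, and that candidates left out would on average be less satisfied. Confidence is moderate.

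Two stronger readings are not supported. One is that the rate will be inflated by some stated number of points: the documents contain nothing from which to estimate how many candidates are passed over or how their satisfaction would differ. The other is that dissatisfied subjects will be lost before the 3-month questionnaire: the plan allows for dropout but does not indicate that dropout is related to satisfaction.

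**What to change.** 1. Replace the sentence in Section 8.2 with a statement that selection, response and no-comparator bias are expected and will be reported as limitations.
2. Invite consecutive candidates who meet Sections 7.2 and 7.3. Keep a log of the numbers screened, declined, and excluded on the surgeon's opinion with the reason, and report it beside the primary result. Surgeon judgement remains part of the criteria; the log makes its use visible.
3. Have subjects complete PROWL themselves, in private, at the start of Visits 1 and 5, before examination or any discussion of results. Tell them that the operating surgeon will not see individual answers during the visit, and handle the forms accordingly. The adverse-event inquiry in Section 13.2 continues unchanged.
4. State that the result describes satisfaction after the procedure in the enrolled patients and does not by itself show an effect of the planning software, and align Section 5 with this.

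The cost is a one-page log, a small change in visit order and data flow, and possibly a lower reported rate with a narrower claim. No added subjects or visits are needed. Items 2 and 3 must be in place before the first candidate is screened.

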9. STUDY PROCEDURE

9.1. Informed Consent / Subject enrollment

No subject will be enrolled into the study who does not meet the inclusion/exclusion criteria and does not sign the current approved informed consent document. Informed consent will be obtained prior to collecting any data for the study. The original signed documents will be maintained by the investigator as a permanent part of the subject's medical records. A signed copy will be provided to the subject.

9.2. Visits and Examinations

Subjects will participate in 3 study visits, including one visit for bilateral surgery. Visits will include an uptake visit, and one operative visit (Visit numbers 1-2 below). The visit schedule, complete with window and associated CRF forms, are displayed in Table 9.2-1. Details of each study visit, including testing to be conducted, are provided below.

Visit Number	Visit Name	Visit Window	CRF Number
1	Preoperative	-90 to 0 days from surgery	1
2	Operative	0 from surgery	2
3	1 Week Postoperative	7 (±3) days postoperative	3
4	1 Months Postoperative	30 (±7) days postoperative	4
5	3 Months Postoperative	90 (±20) days postoperative	5

Table 9.2-1. Visit Schedule

v 1.0

9.2.1. Preoperative

Pre-operative qualification should take place no more than 90 days prior to the LASIK treatment, unless otherwise specified, except for Informed Consent (which must be obtained prior to any protocol-specific non-standard of care assessments). After subjects are consented, they will be qualified for the study (compared with inclusion/exclusion criteria) and assigned a study ID/subject number. Subject numbers will be assigned sequentially at each site in the order of enrollment.

A medical history will be taken and exams will include the tests described below:

- manifest refraction,
- visual acuity,
- slit lamp exam,
- dilated fundus exam,
- topography,
- aberrometry,
- OSDI questionnaire,
- PROWL questionnaire

In addition, all site-specific, routine, usual standard of care preoperative measures should be undertaken.

Measurements should be made as described in section 9.3 below.

9.2.2. Operative (Surgery)

All subjects will undergo bilateral LASIK surgery. The surgeon's usual standard of care with regard to treatment and medication will be used for all study subjects. Surgery planning will be performed using the surgeon's preferred method.

Any adverse events/serious adverse events (AEs/ SAEs) occurring during surgery will be noted at this visit. Any other problems during surgery and comments regarding surgery will be documented.

Any subject whose surgery is not completed successfully will be documented in the appropriate case report form. These subjects will be monitored for safety but clinical performance data may be excluded from the analysis.

9.2.3. Postoperative 1 Week

All routine, usual standard of care postoperative measures should be undertaken. In addition, the subject will undergo VA, manifest refraction, slit lamp examination (Section 9.3). Any device deficiencies or adverse events will be monitored.

9.2.4. Postoperative 1 Month

All routine, usual standard of care postoperative measures should be undertaken. In addition, the subject will undergo VA, manifest refraction, slit lamp examination (Section 9.3). Any device deficiencies or adverse events will be monitored.

9.2.4. Postoperative 3 Month

All routine, usual standard of care postoperative measures should be undertaken. In addition, the subject will undergo VA, manifest refraction, slit lamp examination, dilated fundus exam, topography, aberrometry, and complete the OSDI and PROWL questionnaires (Section 9.3). Any device deficiencies or adverse events will be monitored.

9.2.3. Exit Procedures

In the event of premature exit from the study, all study related examinations should be completed where possible. The Exit CRF should be completed, noting that the subject did not complete the study and the reason for premature study exit. If no premature exit from the study occurs, the Exit CRF should be completed at the end of Visit 5.

9.3. Study Methods and Measurements

All routine testing and basic eye examinations should be carried out at each study visit. Abnormalities should be recorded in the CRF "Comment" section. Specific study examination procedures are outlined below.

9.3.1. Manifest Refraction

Perform a manifest refraction with a high contrast early treatment diabetic retinopathy study (ETDRS) chart under photopic lighting conditions. Document refraction results with sphere, cylinder and axis readings. If uncorrected visual

acuity is not improved by manifest refraction, use zero for sphere and cylinder and draw a line through the blank for the axis.

Note: Each subject should be manually refracted to his/her best correction by an ophthalmologist, optometrist, or a skilled technician using a phoropter or trial lenses.

9.3.2. Visual Acuity (VA)

Distance VA

Measure distance visual acuity using a high contrast ETDRS chart under photopic lighting at a distance of 20 ft.

Conduct testing uncorrected and with the manifest distance refraction in place at all non-surgical visits.

9.4. Unscheduled Visits

Unscheduled exams may be conducted at the discretion of the Investigator with all relevant information from the exam recorded in the source documents and on the Unscheduled Visit pages within the CRF booklet.

9.5. Discontinued Subjects

Discontinued subjects are those who do not have an exit visit or who come into the office to be exited prior to the scheduled final study visit. Subjects may be discontinued from the study at any time if, in the opinion of the investigator, their continued participation in the study poses a risk to their health. The reasons for discontinuation include:

- a. Adverse event;
- b. Lost to follow-up;
- c. Subject decision unrelated to an adverse event;
- d. Protocol violation;
- e. Treatment failure;
- f. Other.

To ensure the safety of all subjects who discontinue prior to Visit 5, investigators should assess each subject and, if necessary, advise them of any therapies and/or medical procedures that might be needed to maintain their health. Any changes in medical health and/or use of concomitant medications should also be captured.

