10. ANALYSIS PLAN

10.1. Analysis Data Sets

All subjects who are enrolled in the study will be evaluated for safety. Efficacy analyses will be performed based on data from those eyes with uncomplicated LASIK surgery.

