10.2. Statistical Methodology

A summary of the data will be prepared for all measurement time points.

For variables measured on a continuous scale, these summaries will include the sample size, as well as the mean, standard deviation, median, minimum, and maximum. For variables measured on a categorical scale, summaries will provide the number and percentage of subjects in each category. These summaries will be provided for all eyes completing the study.

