18. STUDY ENDPOINT CRITERIA

18.1. Patient Completion of Study

If a study patient has completed the final visit (Visit 5) of the study, he/she is considered to have completed the study.

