18.3. Patient Termination

A study patient will be terminated if the study patient develops any severe adverse event that may be related to the study. A study patient will receive appropriate treatment at the discretion of the investigator. Notification of termination will be clearly documented. These study patients are considered to have completed the study and will not be replaced.

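### An undefined treatment-failure exit combined with completer-only percentages can remove poor results from the primary denominator, and sections 10.1 and 10.2 do not agree on that denominator

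*Combined protocol and SAP*

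**What the plan says.** Five parts of the combined protocol and SAP bear on this point.

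- **Exit reasons (9.5).** The list of reasons for discontinuation includes "e. Treatment failure", and no section defines the term. The sentence before the list ties the investigator's discretion to a risk to the subject's health.
- **Summaries (10.2).** After describing number-and-percentage summaries for categorical variables, the section says "These summaries will be provided for all eyes completing the study". It gives no other population for summaries.
- **Completion (18.1).** "If a study patient has completed the final visit (Visit 5) of the study, he/she is considered to have completed the study". Section 18.3 makes one exception, for subjects terminated because of a severe adverse event that may be related to the study: "These study patients are considered to have completed the study and will not be replaced". It does not mention treatment failure.
- **Efficacy set (10.1).** "Efficacy analyses will be performed based on data from those eyes with uncomplicated LASIK surgery". No completion condition appears here.
- **Premature exit (9.2.3, Exit Procedures).** "In the event of premature exit from the study, all study related examinations should be completed where possible". The section does not say whether those data are analysed.

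Sections 9.2.1 to 9.2.4 and Table 15.1 schedule PROWL twice, before surgery and at Visit 5. Section 8.1 defines the primary outcome per subject (percentage satisfied on Q1) and the secondary outcome per eye (spherical equivalent within ±0.50 D). The plan gives no missing-data rule, no rule for counting discontinued subjects as non-responders, and no sensitivity analysis for them.

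**The concern.** LASIK is performed once, at Visit 2, and the later study visits only assess the result. Discontinuing a subject after surgery therefore stops data collection rather than a continuing study treatment. If the reason is that the result was poor, the loss is related to the outcome being measured.

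The study is unmasked, at one site, with no control arm. Its main result is a single percentage, and the stated hypothesis is that this percentage will be high. No comparison group would share the loss and partly offset it. Section 8.2 says that no bias is expected because the study has a single arm, and it offers no safeguard against selective loss. A reader of the final report could not tell whether a completers' percentage and a percentage of all operated subjects differ, because the plan provides for only one of them and leaves open which.

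**Working it through.** **Step 1: the plan's own figures.** The plan gives no expected satisfaction percentage and no expected number of treatment failures. The relevant figures are in section 11: 46 evaluable and 52 enrolled.

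- Inputs: mean paired difference 25, SD of differences 50, power 90%, alpha 5% (taken as two-sided; the plan does not say).
- Standardised effect: 25/50 = 0.5. The exact paired t calculation (noncentral t, noncentrality 0.5 × √n) reaches power 0.900 at n = 44 and 0.913 at n = 46, so 46 is consistent with the stated power.
- Dropout: 46/(1 − 0.10) = 51.1, rounded up to 52. The plan states no rate, but 10% fits. The allowance is 52 − 46 = 6 subjects, or 6/52 = 11.5%.

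The sample-size arithmetic is not at issue. It supplies only N = 52 and an allowance of 6. Section 18.2 replaces subjects lost before surgery, so 52 operated subjects is a reasonable base.

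**Step 2: path of an early exit under each section.**

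- Under 10.2 with 18.1: no Visit 5, so not a completer, so not in the percentages. Because 10.2 covers all measurement time points, that subject's 1-week and 1-month data also leave the summaries.
- Under 10.1: an eye with uncomplicated LASIK stays in the efficacy set whether or not Visit 5 takes place. The plan does not say what value a missing Q1 then takes.

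**Step 3: size for the primary outcome.** Let S be the number satisfied among N = 52 operated, and k the number of not-satisfied subjects who exit before Visit 5.

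- All operated: S/N. Completers: S/(N − k). Difference: S × k / [N × (N − k)].
- Assume S = 45, so 7 are not satisfied: 45/52 = 86.5%.
- k = 1: 45/51 = 88.2% (+1.7 points)
- k = 3: 45/49 = 91.8% (+5.3 points)
- k = 6: 45/46 = 97.8% (+11.3 points)

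S and k are assumptions. If the completers' percentage is instead held between about 80% and 95%, the gap is as follows:

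- one exit: 1.5 points (41/51 against 41/52) to 1.8 points (48/51 against 48/52)
- three exits: 4.6 points (39/49 against 39/52) to 5.5 points (47/49 against 47/52)
- six exits: 9.3 points (37/46 against 37/52) to 11.0 points (44/46 against 44/52)

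**Step 4: direction for the secondary outcome.** Let X of 104 eyes be within ±0.50 D. Losing one subject removes two eyes.

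- Both eyes outside: X/102 > X/104, so the percentage rises.
- One in, one out: (X − 1)/102 > X/104 when X > 52, so it rises in any plausible case.
- Both eyes inside: (X − 2)/102 < X/104 when X < 104, so it falls.

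A dissatisfied subject can have both eyes on target, so the upward direction is likely but not certain.

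**The case against.** The strongest reply is that 10.1, not 10.2, defines the efficacy population, and 10.1 has no completion condition. The completer sentence in 10.2 concerns descriptive summaries and speaks of eyes, while the primary outcome is per subject. This stands in part: the completer denominator is one of two readings, not a settled rule. But 10.2 is the only section that says how percentages are produced, so the ambiguity needs to be resolved before data are seen.

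A reader might infer that treatment failure means a dissatisfied subject, or that investigators are told to exit such subjects. The documents support neither. The term is undefined and could mean something else, such as surgery not completed successfully, which 9.2.2 covers separately. The list in 9.5 includes loss to follow-up, which no investigator elects, so it reads partly as reasons to record. The discretion actually granted rests on health risk. What remains is that an undefined label can be applied to a poor result, and nothing then returns the subject to the percentages.

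Exit data may also exist, because 9.2.3 asks for the examinations where possible and refraction is scheduled at 1 month. That softens the loss, but the plan does not say that such data are used.

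Finally, the numbers may be small. One exit moves the percentage by less than 2 points, against a 95% Clopper-Pearson interval of 74.2% to 94.4% for 45/52. That is fair on size. A confidence interval does not, however, allow for selective loss.

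**Conclusion.** The point holds as a conflict over the denominator with an outcome-related exit attached. Under the completer rule in 10.2, an operated subject exited early for a poor result would leave the primary denominator, and the expected effect is to raise the percentage satisfied. On the illustrative base of 45/52, the rise is about 2 points for one such exit and about 5 for three. The 11-point rise needs six of the seven dissatisfied subjects to exit this way and uses the entire dropout allowance, so it is an extreme case.

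Two stronger readings go too far. One is that both percentages can only be biased upwards. A subject labelled a failure might still report satisfaction, and removing a dissatisfied subject with on-target eyes lowers the ±0.50 D percentage. The other is that a protocol-violation exit has the same effect; nothing in the documents links that reason to outcome.

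The conclusion assumes that 10.2 governs the primary percentage, that at least one exit follows a poor result, and that any exit Q1 is not used.

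**What to change.** 1. Reconcile 10.1 and 10.2. State that the primary denominator is all operated subjects in the efficacy set, whether or not they complete Visit 5, and give its unit (subjects for Q1, eyes for ±0.50 D). Bring 18.1 and 18.3 into line on who counts as a completer.
2. State that PROWL Q1 and refraction obtained at premature exit are used where available, with the time since surgery reported.
3. Count a subject discontinued for treatment failure without any postoperative Q1 as not satisfied. State a rule for Q1 missing for other reasons as well; this point does not settle which.
4. Report the completers' percentage as a sensitivity result, with the number of exits by reason.
5. The sponsor should state what treatment failure means in 9.5 and reconcile it with the health-risk sentence there. The discontinuation rule itself and clinical care are for the sponsor.

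The cost is a few wording changes, one extra table and a possibly less favourable percentage. No visits are added.
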